1 PROTOCOL SUMMARY

Protocol Title	Safer at School Early Alert Hub
Principal Investigator	[name]
Study Sites	University of California, San Diego
Study Activation Date	September 19, 2022
Planned Accrual	Total number of participants - 971
Planned Accrual Period	September 19, 2022 to December 17, 2022
Planned Duration	Data collection period: September 19, 2022 to December 17, 2022 Intervention period: October 3, 2022 to March, 2023
Study Design	Create the Safer at School Early Alert School Hub (SASEA Hub), a school-based environmental surveillance dashboard and diagnostic testing resource hub with an accompanying toolkit for rapid community tailoring to improve COVID-19 testing uptake in vulnerable and underserved communities using a Community Based Participatory Research (CBPR) framework and the Consolidated Framework for Implementation Research (CFIR). We will evaluate the ability of the saseahub.org to increase child and household diagnostic testing uptake via a step-wedge trial, with schools rotated onto the intervention arm (i.e., given access to the saseahub.org) at 2-week intervals. All schools will rotate into the intervention by the Thanksgiving holiday.

Study Objectives	
Aim 1: Create the SASEA Hub, a school-based environmental surveillance dashboard and diagnostic testing resource hub with an accompanying toolkit for rapid community tailoring to improve COVID-19 testing uptake in vulnerable and underserved communities using a Community Based Participatory Research (CBPR) framework and the Consolidated Framework for Implementation Research (CFIR).
 
Aim 2: Assess SASEA Hub's (intervention's) potential to increase diagnostic testing uptake and identify more asymptomatic cases than schools. We will assess this aim through a randomized stepped wedge cluster trial design. The primary outcome will be testing uptake within the past 14-day period, assessed through the SASEA bi-weekly community survey.
 
Aim 3: Assess SASEA Hub's ability to increase risk mitigation behaviors (masking, physical distancing, increased hand hygiene) when the Hub notifies schools of a change in county level COVID-19 case rates or county level wastewater levels

Treatment Description	Intervention – receive access to the community tailored SASEA Hub website
Inclusion Criteria	Parent of a child or staff member attending one of 26 SASEA participating schools
Exclusion Criteria	All non SASEA school participating individuals or students of SASEA participating schools
Study Outcomes	Primary outcome – The primary study endpoint will be student diagnostic testing uptake in the previous 14-days, measured using household surveys distributed at 2-week intervals.

1.1 SCHEMA

Figure 5: Study design

1.2 SCHEDULE OF ACTIVITIES

Our timetable is shown below. Our partner schools will be enrolled as of August 2022, and we will already be implementing SASEA by the time this project begins. We anticipate completing all data collection by the end of Year 1 and will then work with our Community Advisory Board to develop the toolkit, with anticipated dissemination by the next academic school year. Throughout Year 2 we will continue analyzing data related to Aim 4, prepare manuscripts, lay summaries of findings to share with community partners, and applications for next-step work.

	Y 1 Q 1	Y 1 Q 2	Y 1 Q 3	Y 1 Q 4	Y 2 Q 1	Y 2 Q 2	Y 2 Q 3	Y 2 Q 4
Formalize CAB, hire and train staff								
Key informant interviews for template design (n=5)								
Pilot data analysis and dashboard template design with CAB								
Stepped wedge trial with cluster-level dashboard tailoring								
Parent-child interviews (n=40)								
CFIR data analysis and tailoring toolkit development								
Community data dissemination								
Parent-child narrative analysis								
Manuscript writing and dissemination, prepare follow-up applications								

2 INTRODUCTION

2.1 STUDY RATIONALE

The SARS-CoV-2 pandemic necessitated the closure of childcare and school sites around the world. Schools and childcare settings present a unique dilemma for epidemic abatement: As indoor settings where individuals who are not currently eligible for COVID-19 vaccines spend large amounts of time in close proximity to one another they can have very high potential for the virus to spread. Timely detection of asymptomatic infections in school settings is necessary to prevent outbreaks in school settings, particularly asymptomatic outbreaks that could lead to larger community outbreaks among the unvaccinated and/or the evolution of new variants of concern (VoCs) with increased vaccine escape potential. This project will create a unique public-facing dashboard and resource hub (SASEA Hub website) that provides school staff and parents immediate access to environmental testing results from their neighborhood with accompanying information about COVID-19 testing and other related resources. The project will also provide novel information about the potential impact of the dashboard and resource hub on testing practices among students, parents and the broader community.

2.2 BACKGROUND

Public schools are often cornerstones of their community. In historically marginalized communities in particular, they are often trusted providers for a range of support. The tradeoff between these crucial benefits of in-person learning versus the risk of SARS-CoV-2 transmission resulting from in-person learning has been hotly debated throughout much of 2020 and 2021. The stakes are particularly high in historically marginalized communities which rely most heavily on school services but have also been hit the hardest by COVID-19. Individual diagnostic testing combined with contact tracing and behavioral risk mitigation (masking, hand hygiene, ventilation, distancing) is key to reducing SARS-CoV-2 transmission and ensuring safe in-person learning.

The SASEA program was co-developed by the University of California, San Diego (UCSD), the County of San Diego, and 15 partner schools serving socially vulnerable students in 5 school districts. SASEA utilizes daily wastewater and surface (floor) environmental monitoring to detect asymptomatic SARS-CoV-2 infections. Responsive diagnostic testing is immediately triggered by positive environmental samples. In our pilot, SASEA was significantly associated with increased testing uptake among students and staff, and 75% of asymptomatic COVID-19 cases were preceded by a positive environmental sample.

The SASEA Hub intervention offers key innovations in school-community-public health partnership, utilizing anonymous, aggregate, and low-cost environmental surveillance strategies to trigger diagnostic testing, and rapid genetic surveillance with high spatial resolution. Because public schools serve families that reside within a specific geographic catchment area, and because children are likely to have the lowest levels of vaccine uptake even when vaccines become available for children under 12, SASEA Hub schools will provide community sentinel surveillance sites with a high degree of geographic resolution.

In addition to early warning data for students, staff, and parents, increased rates of environmental detection at a SASEA Hub neighborhood, even in the absence of diagnosed cases, can allow public health officials and community stakeholders to rapidly implement increased diagnostic testing and vaccine outreach, and to closely tailor these outreach efforts to the specific community. This project will create a unique public-facing dashboard and resource hub that provides school staff and parents immediate access to environmental testing results from their schools with accompanying information about COVID-19 testing and other related resources. The project will also provide novel information about the potential impact of the dashboard and resource hub on testing practices among students, parents and the broader community.

2.3 RISK/BENEFIT ASSESSMENT

There will be no risk in enrolling to receive text/email notifications for SASEA Hub website updates related to COVID-19 information.

We anticipate that the surveys sent to school parents and staff will hold minimal risk. There is a chance that participants may become emotional, uncomfortable, or bored when completing the survey due to topics concerning COVID-19. There is a small risk that survey data confidentiality could be breached and sensitive information may be exposed. We will not ask for personally identifiable information in these surveys.

2.3.1 KNOWN POTENTIAL RISKS

There will be no risk in enrolling to receive text/email notifications for SASEA Hub website updates related to COVID-19 information.

We anticipate that the surveys sent to school parents and staff will hold minimal immediate and long term risk. There is a chance that participants may become emotional, uncomfortable, or bored when completing the survey due to topics concerning COVID-19. There is a small risk that survey data confidentiality could be breached and sensitive information may be exposed. We will not ask for personally identifiable information in these surveys. No alternative procedures/methods have been considered as the surveys will hold minimal risk.

2.3.2 KNOWN POTENTIAL BENEFITS

Being part of a school enrolled in SASEA Hub will benefit school staff and parents by receiving environmental COVID-19 monitoring updates on their neighborhood along with additional COVID-19 related information on vaccination and testing locations.

ASSESSMENT OF POTENTIAL RISKS AND BENEFITS

There is minimal risk in participating in the intervention – being part of a school receiving the SASEA Hub website. The surveys sent to the school families also hold minimal risk. Being part of a school enrolled in SASEA Hub will benefit school staff and parents by receiving environmental COVID-19 monitoring updates on their neighborhood along with additional COVID-19 related information on vaccination and testing locations.

OBJECTIVES AND ENDPOINTS

OBJECTIVES	ENDPOINTS	JUSTIFICATION FOR ENDPOINTS	PUTATIVE MECHANISMS OF ACTION
Primary			
The primary outcome will be testing uptake among children within the past 14-day period, assessed through the SASEA bi-weekly community survey.	COVID-19 testing in past 14 days among children only	
We will assess this aim through a randomized stepped wedge cluster trial design. The primary outcome will be testing uptake within the past 14-day period, assessed through the SASEA bi-weekly community survey.
 
The SASEA Hub intervention offers key innovations in school-community-public health partnership, utilizing anonymous, aggregate, and low-cost environmental surveillance strategies to trigger diagnostic testing, and rapid genetic surveillance with high spatial resolution.
 
In addition to early warning data for students, staff, and parents, increased rates of environmental detection at a SASEA Hub school, even in the absence of diagnosed cases, can allow public health officials and community stakeholders to rapidly implement increased
	

OBJECTIVES	ENDPOINTS	JUSTIFICATION FOR ENDPOINTS	PUTATIVE MECHANISMS OF ACTION
		diagnostic testing and vaccine outreach, and to closely tailor these outreach efforts to the specific community (i.e., ensure properly translated materials, address testing barriers specific to the community as identified in Aim 1)	

[figure not shown]
STUDY DESIGN

2.4 OVERALL DESIGN

This study uses a mixed-methods convergent participatory design²⁷ (Figure 5). Prior to the stepped wedge trial we will work with our CAB to develop a dashboard and resource hub template. We will then utilize a 20-week randomized stepped wedged trial in 48 school sites with approximately 24,000 students and staff to assess aims 2 and 3. During each 4-week step interval we will use key informant interviews and focus group discussions to tailor the dashboard template to each cluster's specific needs, preferences, and available community resources.

C.4 Aim 1: Create SASEA Hub, a school-based, public facing environmental surveillance dashboard and diagnostic testing resource hub, along with an accompanying toolkit for rapid community tailoring to improve access, acceptability, and implementation of COVID-19 testing in vulnerable and underserved communities using participatory action research to identify (1) core and (2) community-specific barriers to diagnostic testing within and across 4 low income and historically marginalized communities in San Diego County.

Background

Figure 5: Study design

Formative research is necessary to ensure that COVID-19 diagnostic testing, prevention, contact tracing, and isolation strategies are appropriately tailored to the unique needs of underserved and/or socially vulnerable communities. The objective of Aim 1 is to develop an environmental results dashboard and resource hub that can be rapidly tailored for diverse contexts to address COVID-19 diagnostic testing access and acceptability. The toolkit will contain the following components: (1)A customizable dashboard, developed using ArcGIS, for reporting school environmental surveillance results (2)Templates for online and print resources for schools to share with their community that address barriers to diagnostic testing access as well as the potential implications of a positive test; and (3)A toolkit to tailor the dashboard resource hub to specific communities.

C.4.1a Methods to create Product 1

Step 1: Dashboard Template Design

Figure 6: SASEA sample materials

After convening our CAB, we will host a participatory mixed methods data analysis workshop using data from 15 Focus Group Discussions (FGDs) in English and Spanish with 49 parents and staff members from our pilot partner schools, as well as survey data collected from 299 parents and teachers in February of 2020. These data were collected during our pilot phase from November 2020 – March 2021. FGD domains included perceptions of diagnostic testing and contact tracing, barriers to testing access, and preferred strategies for notifications of environmental results. While our team has already reviewed these data internally and begun the process of preparing manuscripts for dissemination, a participatory workshop with our CAB will allow us to more fully incorporate community member insights, providing us with a richer understanding of the data that will support a more responsive public-facing dashboard template design. After the analysis workshop, we will conduct up to 5 additional key informant interviews with school administrators, parent leaders, and county leadership to ensure that our template is responsive to current district, county, and state guidelines.

We will build the dashboard template using ESRI's ArcGIS. This platform is easy to configure, can be embedded in a variety of websites (for example, school or district sites), and can provide real-time data updates on environmental monitoring results pulled from a central server maintained by our team at UCSD and/or the laboratory processing samples. We have already created a dashboard mockup, risk index, and a variety of printable resources as part of our pilot project (Figure 6). We will review and modify these with our CAB based on the data analysis workshop and current local and national guidelines.

Step 2: Community Tailoring

Once we have developed the initial template, we will tailor the dashboard to each school cluster in the 3-4 weeks before a site rotates into the intervention (SASEA Hub) condition using rapid community needs and asset mapping based on the methods developed by Lazarus et al. We will conduct 4 focus group discussions (FGDs) of approximately 8 parents and staff in each cluster. Focus group participants will be asked to participate in a series of activities to identify community needs and assets related to

COVID-19 diagnostic testing uptake and health disparities in their community. The final activities and focus group domains will be determined together with our CAB. Likely activities are shown in table 1.

Table 1: Community mapping exercises

Exercise	Details
1: Community mapping	Participants draw maps of their community to identify needs and assets related to COVID-19 diagnostic testing uptake and related health disparities
2: Health and safety within the (school) community	Participants identify key factors in their community that support or undermine diagnostic testing and/or contribute to related health disparities
3: Contribution of school and community assets to (school) community health and diagnostic testing uptake.	Participants synthesize needs, assets, and factors identified in exercises 1 and 2 to create a community needs and asset ranking matrix.
4: Local action / resource creation	Using the matrix developed in exercise 3, participants identify pre-existing resources that should be included in SASEA-HUB and/or resources that should be created by the CAB and study team (i.e., translations or summaries of key information.)

Step3: SASEA Hub documentation and tailoring toolkit

Throughout the study, we will collect formative process data by meeting regularly with our CAB. We will document the tailoring and academic-community collaboration process using the Consolidated Framework for Implementation Research (CFIR)²⁹ and the Community Based Participatory Research (CBPR) model developed by Belone et al³⁰ as shown in Table 2. Both models recommend regular team meetings and debriefings to reflect on the process of implementation. We will hold regular study team and CAB check-in meetings in which we will reflect on (1) the complexity and logistics of the process, (2) the potential cost of the project and sources for long-term funding (i.e., state grants) (3) the organizational capacity necessary to conduct tailoring data collection and implement the project, and (4) the climate of the project and whether all team members feel equally heard and valued. Similarly, the CBPR model advises study teams to systematically reflect on (1) context, (2) partnership process, and (3) processes and outputs of research. These CBPR and CFIR guided reflections will be recorded using a standardized data collection sheet.

C.4.2.c Analyses for Product 1: We will analyze data for steps 1 and 2 in real time as part of the workshops and focus group discussions. Members of the study team will also record these conversations and take extensive notes throughout to verify any discrepancies that emerge later. After all 4 tailored dashboards (one per school cluster) have been deployed, we will conduct a second round of participatory data analysis workshops with our CAB to identify core similarities and key differences in

the 4 different community need and asset mapping exercises and use these to further refine the dashboard template. We will also analyze the data collected from team debriefings to create a shareable toolkit of best practices for dashboard tailoring.

C.4.3 Expected outcomes and products of Aim 1: The dashboard template and toolkit we generate will be made available on our project website (www.SASEAsystem.org), which already hosts open access laboratory and project implementation protocols for school environmental monitoring.

Table 2: Constructs to create rapid tailoring toolkit

Context

 Resource checklist to identify the knowledge, skills, and capacity necessary to execute project and where they exist within a team Context checklist to assess the political, historical, institutional, and socio-economic issues which are likely to affect the execution of the project. Ethical considerations
Partnership

 Researcher and CAB "bill of rights" Best practices for working with, convening, and reimbursing CAB members Other considerations for ensuring partner equity Ethical considerations
Research

 Logic model identifying which aspects of a program will likely need to be uniquely tailored for a given community and which needs or preferences are likely to be similar across communities Research protocol and field guides for focus group discussions and key informant in-depth interviews Analytic plans for qualitative data Socialstructural Factors Ethical considerations 
 Spatial access Linguistic and cultural tailoring Community-level social vulnerability Sick leave policies Perception of community testing norms

```

graph TD
    Cue[Environmental signal of potential case on campus] --> Desire[Desire to test]
    Self[Self-efficacy] --> Desire
    Desire --> Access[Access COVID-19 Diagnostic Test]
    Testing[Testing Implications] --> Desire
    Testing --> Access
    Contact[Contact Tracing] --> Testing
    Isolation[Isolation] --> Testing
  
```

Figure 4: Testing conceptual framework

C.4.4 Potential problems and contingency plans We recognize that school administrators, parents, and other key stakeholders are likely to have significant time constraints. We have very strong relationships with school districts across the county, as well as the San Diego County Health and Human Services Agency (see letters of support). However, if time constraints do not permit the opportunity for live IDIs, we will instead email our proposed toolkit and questions for written feedback.

SCIENTIFIC RATIONALE FOR STUDY DESIGN

Our conceptual framework is based on our pilot data and behavioral theory (figure 4)

Drawing from both Social Cognitive Theory (SCT) and the Social Ecological Model (SEM), we assume that accessing a COVID-19 diagnostic test is affected by individual self-efficacy and desire to learn one's COVID-19 status, as well as social and structural factors such as geographic access to a testing site, linguistic and cultural tailoring of health outreach efforts, and community level social vulnerabilities (including any local, state, or municipality regulations related to COVID-19 sick leave, unemployment insurance, or rent relief). Desire to test will also be influenced by the perceived implications of testing, whether a desire to know one's status is to protect one's own health and one's community, or a fear of stigma and blame upon diagnosis. Testing implications are also directly related to perceived implications of a positive diagnosis – contact tracing has been linked to fears of data privacy, particularly for those who are undocumented or living in households with mixed documentation status – and tracking and

tracing efforts seem to echo previous alleged government surveillance efforts by the FBI for many ethnic minority Muslim communities. Similarly, a positive test implies the need to isolate with attendant concerns about lost wages, the ability to isolate safely, dependent care, and mental and emotional health during isolation.

In addition to providing resources to address these social and structural factors (i.e., providing downloadable materials in a user's preferred language, linking local to income-replacement or other economic support services) SASEA Hub is also designed to serve as a cue to action via environmental testing data. Environmental testing results and a community risk indicator that incorporates the percentage of students and staff who have consented to responsive testing will be part of the public facing dashboard.

SASEA Hub posits that specific cues to test as a result of concrete risk information (i.e., higher concentrations of COVID-19 particles in wastewater), along with resources to address social and structural barriers to diagnostic testing, is more likely to result in diagnostic testing uptake than (1) offering routine diagnostic testing in the absence of environmental cues, and (2) environmental cues alone with no resources to offset structural barriers.

JUSTIFICATION FOR INTERVENTION

Formative research is necessary to ensure that COVID-19 diagnostic testing, prevention, contact tracing, and isolation strategies are appropriately tailored to the unique needs of underserved and/or socially vulnerable communities. The objective of Aim 1 is to develop an environmental results dashboard and resource hub that can be rapidly tailored for diverse contexts to address COVID-19 diagnostic testing access and acceptability. The toolkit will contain the following components: (1)A customizable dashboard, developed using ArcGIS, for reporting regional environmental surveillance results (2)Templates for online and print resources for schools to share with their community that address barriers to diagnostic testing access as well as the potential implications of a positive test; and (3)A toolkit to tailor the dashboard resource hub to specific communities.

We will utilize a 20-week randomized stepped wedged trial in 48 school sites with approximately 24,000 students and staff to assess aims 2 and 3. During each 4-week step interval we will use key informant interviews and focus group discussions to tailor the dashboard template to each cluster's specific needs, preferences, and available community resources. The stepped wedged trial will allow all participants to eventually access this COVID-19 tool to help them assess their risk and choose mitigation strategies. It would be unethical to restrict information of this kind from some participants.

END-OF-STUDY DEFINITION

A participant is considered to have completed the study if she or he has completed the community survey.

STUDY POPULATION

INCLUSION CRITERIA

In order to be eligible to participate in this study, an individual must meet all of the following criteria:

1. Parent with children enrolled at any of the 50 schools across the San Diego County that participated in the study during the 2021-2022 school year.
2. School staff working at any of the 50 schools across the San Diego County that participated in the study during the 2021-2022 school year.
3. Provision of signed and dated informed consent form
4. Access to necessary resources for participating in a technology-based intervention (i.e., computer, smartphone, internet access)

EXCLUSION CRITERIA

An individual who meets any of the following criteria will be excluded from participation in this study:

1. Not affiliated with participating sites as parents or staff.
2. No access to necessary resources for participating in a technology-based intervention (i.e., computer, smartphone, internet access)

LIFESTYLE CONSIDERATIONS

N/A

SCREEN FAILURES

N/A

STRATEGIES FOR RECRUITMENT AND RETENTION

This study will consist of a 20-week randomized stepped wedge cluster trial. Parents will be invited to participate in a 5–10-minute self-administered survey conducted at 4-week intervals. Prospective parent participants will be identified using a sampling frame provided by schools, at the beginning of the school year, consisting of classroom, classroom size, and grade level. Between 40 participating schools clustered and 8 childcare sites within 4 district clusters (approximately 12 sites per district cluster) will be enrolled during the study; for a total of 48 sites and 4 district clusters. The average size of school and childcare sites is 500. From the sampling frame, three classrooms within each school will be randomly selected. Within the randomly selected classroom, teachers will distribute a survey invitation to all students. Average class size is 25 and we anticipate a 25% response rate per class, resulting in approximately 20 surveys per site or approximately 150 surveys per cluster. Random samples of classrooms will be selected every 2-weeks with replacement using a randomization schedule generated by the study.

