3.3 POPULATIONS FOR ANALYSES

A random cross-sectional sample of parents and caregivers will be selected to participate in a 5–10-minute self-administered survey conducted at 4-week intervals (see Table 3). Prospective parent participants will be identified using a sampling frame provided by schools, at the beginning of the school year, consisting of classroom, classroom size, and grade level. From the sampling frame, three classrooms within each school will be randomly selected. Within the randomly selected classroom, teachers will distribute a survey invitation to all students. Average class size is 25 and we anticipate a 15% response rate per class, resulting in approximately 12 surveys per school or approximately 144 surveys per cluster; equating to 2,880 parent surveys during the 20-week period. Random samples of classrooms will be selected every 4-weeks with replacement using a randomization schedule generated by the study biostatistician, [name]. To increase generalizability, we will randomly select serial cross-sectional samples with replacement since serial samples will allow for greater representation given the likelihood of student absences on the day of recruitment (e.g., potential for individual students to be absent and/or classrooms to be quarantined due to COVID-19 exposure).

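### The survey-yield figures contradict each other, and the 2,880 surveys in the household-testing power statement do not match the planned accrual of 971

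*Combined protocol and SAP*

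**What the plan says.** Every section that describes the survey sampling uses the same scheme: "three classrooms within each school will be randomly selected", "Average class size is 25", and all students in the selected classes are invited. The sections then differ on yield.

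- **Strategies for Recruitment and Retention:** "we anticipate a 25% response rate per class, resulting in approximately 20 surveys per site or approximately 150 surveys per cluster". This section has about 12 sites in each of 4 clusters, 48 in all. It puts the survey at 4-week intervals but draws classrooms every 2 weeks.
- **Administration and/or Dosing, and section 3.3:** "we anticipate a 15% response rate per class, resulting in approximately 12 surveys per school or approximately 144 surveys per cluster". Both sections put the total over the 20 weeks at 2,880. Classrooms are drawn every 4 weeks.
- **Section 3.2:** 2,880 parents are the sample for over 80% power to detect 2.0% against 4.8% in household testing, which this section labels secondary. Its power statement for what it calls the primary outcome uses 500 staff and students per school instead.
- **Protocol Summary:** "Total number of participants - 971", with 26 participating schools and surveys every 2 weeks. No derivation is given.

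The amendment history records a single version, so all of this is current text.

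**The concern.** One sampling procedure carries two response rates, and one of the two yield chains fails on its own inputs. Site staff cannot tell whether to expect about 20 or about 12 surveys per site per round.

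The survey total behind a stated power is also about three times the planned accrual. This matters beyond the secondary label in section 3.2, because the Protocol Summary and the objectives table measure the primary endpoint by survey. The survey total therefore sets the precision of the primary analysis as those sections define it.

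**Working it through.** **Inputs from the documents.** 3 classrooms per school; 25 pupils per class; response 25% (recruitment section) or 15% (Administration and/or Dosing, section 3.3); 12 sites per cluster; 4 clusters; 5 rounds (20 weeks at 4-week intervals); ICC 0.10, type I error 0.05 and rates 2.0% and 4.8% (section 3.2).

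**1. Reproducing 2,880.** 12 per school × 12 schools × 4 clusters × 5 rounds = 2,880. The chain is exact once 12 per school is accepted.

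**2. The 15% chain without early rounding.** 3 × 25 × 0.15 = 11.25 per school. Then 11.25 × 12 = 135 per cluster, and 135 × 4 × 5 = 2,700. The stated total is 180 higher (180 / 2,700 = 6.7%).

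**3. The 25% chain.** 3 × 25 × 0.25 = 18.75 per site. Then 18.75 × 12 = 225 per cluster, or 20 × 12 = 240. The stated 150 is 33% below 225 and 37.5% below 240. Reaching 150 means changing a stated input: 8 sites (18.75 × 8 = 150), 2 classrooms (12.5 × 12 = 150), or a 16.7% response.

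**4. Totals over 5 rounds.** At 15%: 2,700 (2,880 rounded). At 25%: 225 × 4 × 5 = 4,500 (4,800 rounded). Drawing every 2 weeks would give 10 rounds and double the unrounded totals to 5,400 and 9,000.

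**5. The planned accrual.** 971 / 2,880 = 34%. Some products come close, such as 20 × 48 × 1 = 960 and 18.75 × 26 × 2 = 975. The documents state neither, and one or two rounds contradict the multi-round plan.

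**6. Effect on power for 2.0% against 4.8%.** Hussey-Hughes variance with schools as clusters, 48 schools (I), 4 sequences of 12, 5 periods (T), and a two-sided test (assumed). With m surveys per school-period and total variance v: τ² = 0.10v and σ² = 0.90v / m.

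Design sums:
- U = 12 × (4 + 3 + 2 + 1) = 120
- W = 12² + 24² + 36² + 48² = 4,320
- V = 12 × (16 + 9 + 4 + 1) = 360
- IU − W = 1,440
- U² + ITU − TW − IV = 14,400 + 28,800 − 21,600 − 17,280 = 4,320

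Var = 48σ²(σ² + 5τ²) / (1,440σ² + 4,320τ²), and power = Φ(0.028 / √Var − 1.96).

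The documents do not say which v was used, so two conventions are shown: the average of the two binomial variances, (0.0196 + 0.045696) / 2 = 0.032648, and the baseline variance, 0.0196.

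| Surveys | m = surveys / (48 × 5) | Power, averaged v | Power, baseline v |
|---|---|---|---|
| 2,880 | 12 | 0.71 | 0.90 |
| 2,700 | 11.25 | 0.68 | 0.88 |
| 4,500 | 18.75 | 0.87 | 0.98 |
| 971 | 4.05 | 0.33 | 0.51 |

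Worked line for 971, averaged v: τ² = 0.0032648 and σ² = 0.0293832 / 4.0458 = 0.0072626. Var = 0.34860 × 0.023587 / 24.562 = 0.00033476, so SE = 0.0183. Then 0.028 / 0.0183 = 1.53, and Φ(1.53 − 1.96) = 0.33.

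**The case against.** Much can be said for the plan, and several parts of it stand.

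- **A reader might infer that the trial's power rests on the faulty 25% line.** It does not. The figures of 25%, 20 and 150 enter no power calculation. The 2,880 supports only the outcome that section 3.2 calls secondary.
- **A reader might infer that rounding 11.25 to 12 breaks the 80% claim.** It does not. The text says the figure is approximate, and 3.75 per class rounds to 4, which gives 12 for three classes. The cost is about 2 to 3 points of power. Whether 2,880 itself exceeds 80% depends on the variance convention (0.71 or 0.90), not on the rounding.
- **A reader might work back from 971 and 26 schools to a response rate.** The documents do not support this. The classroom sampling belongs to the 48-site, 20-week plan. The number of waves in the 26-school study would have to be inferred, and the Protocol Summary's inclusion criterion also admits staff.
- **The units may differ.** 971 counts participants, while 2,880 counts surveys sampled with replacement. The power figure for 971 is therefore conditional on reading 971 as the number of surveys.
- **The two per-cluster figures nearly agree.** About 150 and about 144 differ by 4%. But the larger figure does not follow from the rate and the per-site yield beside it, so the agreement does not settle which inputs are meant.

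None of this explains 25% against 15%, 150 against 225 to 240, or where 971 comes from.

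**Conclusion.** The yield figures need to be reconciled. Two conclusions need only multiplication of stated inputs: the recruitment section's per-cluster figure is 33% to 37.5% below what its own inputs give, and the response rate for one procedure is stated as both 25% and 15%. Planned accrual is about one third of the survey total used for the household-testing power statement, and it has no derivation.

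The power consequence is conditional. It assumes 971 surveys spread evenly over the 48-school, 5-period design, ICC 0.10 and a two-sided 0.05 test. Power would then be about 33% to 51%, against the claimed level of over 80%. The documents give no calculation for 26 schools, and none was made here. This is an inconsistency in the plan's stated targets and does not show that the study will fail to recruit.

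**What to change.** Choose one school count, one response rate, one survey interval and one number of waves. Derive the expected total once, as schools × 3 classrooms × 25 × response rate × waves, and round only at the end. Use that total in the Protocol Summary, Strategies for Recruitment and Retention, Administration and/or Dosing, and sections 3.2 and 3.3, replacing the 25%, 20 and 150 figures. If accrual is to be counted in participants, or to include staff, say so and state how it relates to the number of surveys.

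Then restate in section 3.2 the power or minimal detectable difference for that total and school count, giving the variance convention and the sidedness of the test.

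The cost is edits to five sections and one rerun of the power calculation. If the smaller totals apply, stated power becomes less favourable: by about 2 to 3 points if the total is 2,700, and substantially if 971 is the real target.
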